13. TECHNOLOGY TRANSFER

No technology transfer agreement is in place for this protocol.

APPENDIX A: World Health Organization Bleeding Scale

	Grade 1	Grade 2	Grade 3	Grade 4
Oral	 Oropharyngeal bleeding – total duration of all episodes in previous 24 hours 30 minutes* Petechiae of oral mucosa Epistaxis – total duration of all episodes in previous 24 hours 30 minutes* 	 Oropharyngeal bleeding – total duration of all episodes in previous 24 hours > 30 minutes* Epistaxis – total duration of all episodes in previous 24 hours 30 minutes* 	Any bleeding requiring RBC transfusion over routine transfusion needs [†]	Any bleeding associated with severe hemodynamic instability (hypotension; >50mm/Hg fall or >50% decrease in either systolic or diastolic blood pressure,
Skin, soft tissue, musculoskeletal	 Petechiae of skin Purpura ≤1 inch diameter One or more spontaneous hematomas in the soft tissue or muscle > 1 inch 	 Purpura > 1 inch diameter Spontaneous hematoma in deeper tissues Joint bleeding (confirmed by aspiration, imaging study or other accepted technique) 	Any bleeding requiring RBC transfusion over routine transfusion needs [†]	with associated tachycardia (heart rate increase of ≥20% for 20 minutes) and requiring RBC transfusion over
Gastrointestinal	Positive stool occult blood test	 Melanotic stool Hematochezia – visible red blood mixed in stool, not requiring a transfusion Hematemesis – grossly visible blood in emesis or in nasogastric drainage tube (not related or secondary to swallowed blood) 	Any bleeding requiring RBC transfusion over routine transfusion needs [†]	 routine transfusion needs Fatal bleeding from any source Retinal bleeding with visual impairment (Visual impairment is defined as source to be for the former of the former
Genitourinary	 Any biochemical or microscopic Hb/RBCs without red urine‡ Abnormal vaginal bleeding (Unexpected bleeding out of normal cycle or bleeding heavier than normal or breakthrough bleeding (patient on hormonal therapy to prevent bleeding)) with spotting 	 Gross/visible hematuria without need for transfusion Abnormal vaginal bleeding (Unexpected bleeding out of normal cycle or bleeding heavier than normal or breakthrough bleeding (patient on hormonal therapy to prevent bleeding)) more than spotting 	Any bleeding requiring RBC transfusion over routine transfusion needs†	 a field deficit, and patients with suspected visual impairment require an ophthalmologic consult for documentation) CNS symptoms with non- traumatic bloody lumbar
Pulmonary		 Hemoptysis – visible blood Blood in broncho-pulmonary lavage, or blood tinged sputum (excluding those with nose or oropharyngeal bleeding) 	Any bleeding requiring RBC transfusion over routine transfusion needs [†]	 Puncture CNS bleeding on imaging study with or without dysfunction
Body cavity		 Visible blood in body cavity fluid (e.g. red cells apparent in fluid aspirate) short of criteria for Grade 3 or 4 	Grossly bloody body cavity fluids and organ dysfunction with symptoms, and/or need to intervene (e.g. to aspirate), and/or need for transfusion	
Central nervous system		 Retinal bleeding without visual impairment Lumbar puncture with blood (>5 RBC/mL in CSF on microscopic analysis and non-traumatic tap), no symptoms and no visible red color 	Lumbar puncture with visible red color in absence of symptoms, and non-traumatic tap	
Invasive sites		 Bleeding at invasive sites (venipuncture sites, intravenous lines or catheter exit sites): active oozing at site for a cumulative total of >1 hour in the previous 24 hours 	Any bleeding requiring RBC transfusion over routine transfusion needs [†]	
Hemodynamic instability			Any bleeding associated with moderate hemodynamic instability (hypotension; >30mmHg fall or >30% decrease in either systolic or diastolic blood pressure) and requiring RBC transfusion over routine transfusion needs [†]	

RBC indicates red blood cell; Hb, hemoglobin; CSF, cerebrospinal fluid; Hg, mercury; and CNS, central nervous system †Red cell transfusion must be specifically related to treatment of bleeding within 24 hours of onset of bleeding *Count actual bleeding (i.e. "running out" or need for basin, Kleenex, towel, etc.) not minor bleeding ‡Not assessed in PLADO

APPENDIX B: Protocol Worksheet

The SOLID Platelet Study, Protocol #19-CC-0005

LONG Transfusion followed by SHORT Transfusion

INSTRUCTIONS:

- All CBCs should be collected in a 2 mL EDTA tube; please WASTE the first 1 mL at each sample collection
- CBC collection times may occur (+/-) 15 minutes of the target draw time
- Documenting 'EXPECTED TIME' is optional; it is provided as a reference tool for planning the CBC collection and transfusion START / STOP Schedule
- Please call [name] (DTM, Protocol PI) with any questions, concerns, or if you run in to any problems, at [contact].

		EXPECTED TIME	ACTUAL TIME	PLATELETS	HEMOGLOBIN	
		(Optional)		(10 ⁹ /L)	(g/DL)	
1.	PRE (0-HOUR)					
	i. START Long Transfusion AFTER CBC collect	tion				
	ii. Continue transfusing over 4-HOURS					
	iii. Gently Swirl Bag for 20 revolutions every	30-min				-
	A. CBC COLLECTION					
	B. LONG TRANSFUSION START					
2.	2-HOUR (1b) + 2-HOURS					
	A. CBC COLLECTION					-
3.	4-HOUR (1b) + 4-HOURS - STOP Long Transfusion B	EFORE CBC Collection				TOE
	A. LONG TRANSFUSION STOP					BEO
	B. CBC COLLECTION					COMPLETED
4.	6-HOUR (1b) + 6-HOURS				≤P	
	i. START Short Transfusion AFTER CBC Collection					Ē
	ii. Also serves as the PRE (0-HOUR) CBC for	the Short Transfusion Tr	ansfuse for no more			Ē
	than 60-minutes					
	iii. Gently Swirl Bag for 20 revolutions every	30-minutes				
	A. CBC COLLECTION					BY DTM
	B. SHORT TRANSFUSION START					>
5.	7-HOUR (4b) + 1-HOUR - STOP Short Transfusion					
	A. SHORT TRANSFUSION STOP					
6.	8-HOUR (4b) + 2-HOURS					-
	A. CBC COLLECTION					-
7.	10-HOUR (4b) + 4-HOURS	1			-	-
	A. CBC COLLECTION					-
8.	12-HOUR (4b) + 6-HOURS					
	A. CBC COLLECTION					
		1				

Print Name of RN(s) Completing form	Signature	Date
1)		
2)		

APPENDIX C: Protocol Worksheets

The SOLID Platelet Study, Protocol # 19-CC-0005

SHORT Transfusion followed by LONG Transfusion

GROUP	BLOCK	Date (mm-dd-yy)	Randomly Assigned ID	PATIENT CRIS LABEL
				×

INSTRUCTIONS:

- All CBCs should be collected in a 2 mL EDTA tube; please WASTE the first 1 mL at each sample collection
- CBC collection times may occur (+/-) 15 minutes of the target draw time
- Documenting 'EXPECTED TIME' is optional; it is provided as a reference tool for planning the CBC collection and transfusion START / STOP Schedule
- Please call [name] (DTM, Protocol PI) with any questions, concerns, or if you run in to any problems, at [contact].

		EXPECTED TIME (Optional)	ACTUAL TIME	PLATELETS (10 ⁹ /L)	HEMOGLOBIN (g/DL)	
1.	PRE (0-HOUR)	(Optional)		(10-71)	(g/DL)	
1.	i. START Short Transfusion AFTER CBC collection					
	ii. Transfuse for no more than 60-minutes					
	iii. Gently swirl bag for 20 revolutions every 30-m	inutes				
	A. CBC COLLECTION					
	B. SHORT TRANSFUSION START					
2.	1-HOUR (1b) + 1-HOUR - STOP Short Transfusion					
	A. SHORT TRANSFUSION STOP					
3.	2-HOUR (1b) + 2-HOURS					
	A. CBC COLLECTION					FOE
4.	4-HOUR (1b) + 4-HOURS					TO BE COMPLETED BY DTM
	B. CBC COLLECTION					M
5.	6-HOUR (1b) + 6-HOURS					Ē
	i. START Long Transfusion AFTER CBC Collection				B	
	ii. Also serves as the PRE (0-HOUR) CBC for the L	ong Transfusion				BY E
	iii. Continue transfusing over 4-HOURS					DTM
	iv. Gently swirl bag for 20 revolutions every 30-n	ninutes				
	A. CBC COLLECTION					
	B. LONG TRANSFUSION START					
6.	8-HOUR (4b) + 2-HOURS		1			
	A. CBC COLLECTION					
7.	10-HOUR (4b) + 4-HOURS					
	A. LONG TRANSFUSION STOP					
	B. CBC COLLECTION					
8.	12-HOUR (4b) + 6-HOURS					
	A. CBC COLLECTION					

Print Name of RN(s) Completing form	Signature	Date
1)		
2)

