6.3. Treatment Monitoring

6.3.1. CBC Collection

All CBC blood draws will be collected in a 2 ml EDTA tube, after wasting the first 1ml of blood drawn. The sample should be obtained via the patient's peripheral access device, but a peripheral venipuncture or draw from the patient's central access device may be done if access the patient's peripheral line is not feasible. The initial 1 ml sample discard, prior to filling the 2ml EDTA tube, is to prevent a false reading by drawing the sample from the same line through which the patient is receiving the transfusion.

Patients will have platelet counts obtained by CBCs collected at the following scheduled intervals:

- 1) Pre-transfusion (0-HOUR) CBC: obtained 15-minutes prior to transfusion start time
- 2) 2-HOUR CBC: Obtained +/- 15-minutes of the 2-HOUR mark after the infusion start time

- 3) 4-HOUR CBC: Obtained +/- 15-minutes of the 4-HOUR mark after the infusion start time
- 4) 6-HOUR CBC: Obtained +/- 15-minutes of the 6-HOUR mark after the infusion start time. Also serves as the PRE (0-HOUR) CBC for the subsequent, transfusion; the subsequent transfusion will also have scheduled CBCs drawn at q2hr intervals (i.e. CBC at 8-HOUR, 10-HOUR, 12-HOUR), collected +/- 15-minutes of each time mark)

CBCs unable to be obtained as indicated will result in an unsuccessful, or "failed," block. Failed blocks will be precluded from further analysis. All attempts will be made to repeat the block as soon as clinically possible. Blood draws for other clinical purposes should be avoided, but will not result in a failed block unless it/they preclude the aforementioned scheduled CBCs needed for this protocol's treatment monitoring.

From the CBC, platelet value will be used to calculate the platelet AUC using the trapezoid rule and adjusted for the absolute number of platelets transfused, on a rolling basis for each transfusion.

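### Appendix C times the Long-period CBCs and the Long stop from entry 4b, the Short period's 4-hour CBC, so the worksheet contradicts its own hour labels by 2 hours

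*Combined protocol and SAP*

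**What the plan says.** Section 6.2.1 assigns Group B to Short then Long in the first block and alternates the order in later blocks. Appendix C is the worksheet for that order.

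On Appendix C, entry 1b is the Short start. Step 4 is headed "4-HOUR (1b) + 4-HOURS"; its only entry is lettered B and is a CBC collection. Step 5 is headed "6-HOUR (1b) + 6-HOURS", has "B. LONG TRANSFUSION START" as its second entry and carries the instruction "Continue transfusing over 4-HOURS". The next three rows are:

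- step 6, "8-HOUR (4b) + 2-HOURS": a CBC;
- step 7, "10-HOUR (4b) + 4-HOURS": the Long stop and a CBC;
- step 8, "12-HOUR (4b) + 6-HOURS": a CBC.

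Section 6.2.2 sets the Long infusion at 4 hours. Section 6.3.1 times each draw from the start of the infusion it belongs to, for example "4-HOUR CBC: Obtained +/- 15-minutes of the 4-HOUR mark after the infusion start time", and lists the second infusion's draws at block hours 8, 10 and 12. Section 8.1 builds the primary outcome from the counts at 0, 2, 4 and 6 hours after each infusion starts, and compares the two infusions of the first block.

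**The concern.** The reference to 4b looks carried over from Appendix B. On that form step 4 is the 6-hour row and 4B is the start of the second infusion, so the reference works. Appendix C gives the Short stop its own row as step 2. The 6-hour row therefore becomes step 5 and the second infusion's start becomes 5B, but the last three rows still cite 4b.

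Nothing flags the slip as a dead reference, because 4b exists on Appendix C and has a clock time entered against it. Section 6.3.2 names these worksheets among the places where transfusion duration and CBC times are recorded, so the form governs data for the primary endpoint. The conflict touches only the Long dose and only the Short-then-Long order. Any effect would fall on one arm in one sequence.

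**Working it through.** **Inputs.** Appendix C: 1b = hour 0; step 4 at 1b + 4 h; step 5 at 1b + 6 h; steps 6 to 8 at 4b + 2, + 4 and + 6 h. Appendix B: step 4 at 1b + 6 h; later rows at 4b + 1, + 2, + 4 and + 6 h. Draw window: 15 minutes either side (section 6.3.1 and both worksheets).

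**Appendix B as a control.** 4b = 0 + 6 = hour 6. The later rows fall at 6 + 1, 6 + 2, 6 + 4 and 6 + 6 = hours 7, 8, 10 and 12, which match its labels.

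**Appendix C.** As printed, 4b = 0 + 4 = hour 4. The Long start, 5B, is 0 + 6 = hour 6.

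| Row | Label | From 4b as printed | From 5B | Literal time after Long start |
|---|---|---|---|---|
| Step 6, CBC | 8 | 4 + 2 = 6 | 6 + 2 = 8 | 0 h |
| Step 7, Long stop and CBC | 10 | 4 + 4 = 8 | 6 + 4 = 10 | 2 h |
| Step 8, CBC | 12 | 4 + 6 = 10 | 6 + 6 = 12 | 4 h |

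Each literal time is 2 hours before its label, and 120 / 15 = 8 times the window. Counting from 5B reproduces all three labels and the hours in section 6.3.1. The literal stop falls 2 hours into an infusion that step 5 and section 6.2.2 set at 4 hours. The Long start is keyed to 1b and stays at hour 6.

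**What literal use would do to the AUC.** The draws would fall at 0, 2 and 4 hours after the Long start, with none at 6 hours, so the 0-to-6-hour AUC could not be formed from correctly timed counts.

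Suppose instead that those counts were entered as the 2-, 4- and 6-hour values. Assume a constant rate, equal recovery and first-order clearance at rate k = ln 2 / half-life. Per unit dose, the count t hours into a 4-hour infusion is (0.25/k)(1 − e^(−kt)), or t/4 with no clearance. With 2-hour spacing and a baseline of 0, the trapezoid AUC is 2 × (second + third + half the fourth count).

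- No clearance, correct timing: counts 0, 0.5, 1, 1; AUC = 2 × (0.5 + 1 + 0.5) = 4.0.
- No clearance, mis-timed, full infusion: 0, 0, 0.5, 1; AUC = 2 × (0 + 0.5 + 0.5) = 2.0, a fall of 50%. The falls are 44% at a 4-hour half-life (2.80 to 1.57) and 39% at 2 hours (2.07 to 1.26).
- No clearance, mis-timed and stopped at 2 hours: 0, 0, 0.5, 0.5; AUC = 2 × (0 + 0.5 + 0.25) = 1.5. Half the dose has been given. Divided by the dose delivered, 1.5 / 0.5 = 3.0, a fall of 25%. The corresponding falls are about 18% at a 4-hour half-life (1.14 / 0.5 against 2.80) and 13% at 2 hours (0.90 / 0.5 against 2.07). If the full bag content were the divisor, the falls would be 63%, 59% and 57%.

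These figures show only how much the result depends on what staff do and how the dose is counted. They are not expected effects.

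**The case against.** The strongest reply is that this is a clerical slip which the page itself resolves. Each affected row leads with an hour label that agrees with section 6.3.1. Step 5 states the duration. The literal step 6 time coincides with the Long start, when a pre-infusion CBC is already due, so the clash is easy to notice. The form calls the expected-time field optional, has a column for actual times and tells staff to call with questions. A draw 2 hours early is far outside the window. Under section 6.3.1 the likelier result is a failed block, excluded and repeated if possible, rather than a silent bias.

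Most of this stands. A reader might infer that following the form moves the whole Long schedule 2 hours early in every Group B first block. The documents do not support that: the Long start does not move, the same rows carry conflicting labels, and nothing shows that staff would prefer the parenthesis to the label. A reader might also infer a bias of about half or more against Long. That needs mis-timed counts to be entered at the wrong times despite the recorded actual times. The falls of 57% to 63% also need an undelivered half-dose to be counted as given, although section 8.1 adjusts for platelets transfused. Its bag-weight method might count the full bag, but the plan does not say how a part-given bag is handled.

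The labels do not settle everything, however. They count hours from the start of the block, whereas section 6.3.1 counts from the start of each infusion. If, as an assumed example, Long began 30 minutes after the 6-hour mark, a draw at block hour 8 would be 1.5 hours into Long, outside the window. The parenthesis is the part of the row heading that ties these rows to the actual second start, and it cites the wrong entry.

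**Conclusion.** The concern holds as an internal contradiction in Appendix C. Three cross-references give times 2 hours before their own labels, and one of them places the Long stop in conflict with the stated duration. This follows from the step numbering alone.

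Exposure covers Group B first blocks, about half of those in the primary analysis. It also covers Short-then-Long later blocks (the second in Group A, the third in Group B), which feed only secondary analyses. Whether any block would be mis-timed depends on staff using the printed arithmetic. If they did, a block could fail or mis-timed Long values could enter the AUC; the size of any bias is conditional and not established. The test, the sample size and the schedule in the protocol body are unaffected. Severity is minor to moderate: the slip is simple, but it sits on the form that times one arm's primary-endpoint draws.

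**What to change.** Reconcile the cross-references in Appendix C steps 6, 7 and 8 with the step that records the Long start (5B on that form), the printed hour labels and sections 6.2.2 and 6.3.1, and reissue the worksheet. Optionally, reletter the lone entry in step 4 as A, as in Appendix B's single-entry rows, so that 4b no longer points to a live line.

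For any block already run on this form, compare the recorded Long stop and the three later CBC times with the recorded Long start before accepting the block as successful.

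The cost is three references on one page, a reissue, and a check of completed Short-then-Long worksheets. The statistical analysis does not change.
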